## 7.3. Vital Signs

Vital signs (systolic and diastolic blood pressures, heart rate, and respiratory rate) will be measured at Baseline, Week 8, Session 2 Light Session visit prior to the light session and during the End of Study follow-up visit.

For vital signs summaries, the Baseline values will be defined as the assessment obtained at Baseline assessment.

Vital signs data and change from Baseline will be summarized using descriptive statistics.

Criteria for clinically significant values have been defined as shown in [Table 7](#). For each vital sign variable, clinically significant value at Baseline and minimum and maximum clinically significant values during Treatment Cycles will be identified. Shift in number of patients with clinically significant values at baseline to the number of patients with minimum and maximum clinically significant values on-therapy will be displayed.

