#### 4.4.4 Vital Signs

Vital signs will be obtained by site personnel at Baseline, Week 8 Session 2 Light Session visit prior to the light session and during the End of Study follow-up visit. Vital signs obtained will consist of:

- Resting Blood Pressure
- Heart Rate
- Respiratory Rate

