**Table 7: Vital Signs Clinically Significant Values**

Vital Sign Variable	Absolute Value
Systolic Blood Pressure	$\geq 180$ mmHg and increase of $\geq 20$ mmHg from baseline $\leq 90$ mmHg and decrease of $\geq 20$ mmHg from baseline
Diastolic Blood Pressure	$\geq 105$ mmHg and increase of $\geq 15$ mmHg from baseline $\leq 50$ mmHg and decrease of $\geq 15$ mmHg from baseline
Pulse	$\geq 120$ bpm and increase of $\geq 15$ bpm from baseline $\leq 50$ bpm and decrease of $\geq 15$ bpm from baseline

Listings of all vital sign values will be presented.

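### Every vital-sign criterion in SAP Table 7 requires a change from baseline, so the 'clinically significant at baseline' row of the planned shift table is always zero and pre-existing abnormality cannot be told from new abnormality

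*SAP*

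**What the plan says.** SAP 7.3 refers to Table 7 for the definition of a CS vital sign and takes the Baseline visit assessment as the baseline value. It asks that CS values be identified at Baseline, and that minimum and maximum CS values be identified during treatment cycles. It then plans an on-therapy comparison, described as "Shift in number of patients with clinically significant values at baseline to the number of patients with minimum and maximum clinically significant values".

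Table 7 gives a high and a low rule for systolic pressure, diastolic pressure and pulse. Its column is headed 'Absolute Value', but each rule has two parts joined by 'and': a limit and a change from baseline. The high blood-pressure rules, for example, join them with "mmHg and increase of".

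On timing, SAP 4.4.4 says: "Vital signs will be obtained by site personnel at Baseline, Week 8 Session 2 Light Session visit prior to the light session", and then adds the End of Study follow-up visit. SAP 4.2 places End of Study 2 weeks after completion of therapy. SAP 3 describes a single 8-week course of twice-weekly treatment.

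**The concern.** A shift table separates patients who were already past a limit before treatment from those who passed it afterwards. That needs a flag that can be positive at baseline. A rule that contains a change from baseline cannot supply one, so the table's starting category is fixed before any data are collected.

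The trial has no control arm, so each patient's own baseline is the only comparator for vital signs, which are part of the secondary endpoint (SAP 4.2; protocol 3.2). A patient with an extreme reading before the first application would enter the table as not CS, and a later extreme reading could be counted as having emerged on treatment.

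The on-therapy side is also unclear. The section speaks of cycles and of minimum and maximum values, which implies repeated readings within a treatment period. Two programmers could reasonably build different tables from it.

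**Working it through.** The SAP states no figure for this display, so there is none to reproduce. The check is of the rule itself.

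**Inputs (SAP Table 7 and 7.3).** A value is CS if it meets either rule for its variable:
- Systolic: at least 180 with a rise of at least 20 mmHg, or at most 90 with a fall of at least 20 mmHg.
- Diastolic: at least 105 with a rise of at least 15 mmHg, or at most 50 with a fall of at least 15 mmHg.
- Pulse: at least 120 with a rise of at least 15 bpm, or at most 50 with a fall of at least 15 bpm.
- Baseline: the Baseline visit value. The general definition in SAP 5.4 (last value before first dose) leads to the same result.

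**Step 1: the flag at baseline.** Change at baseline = baseline − baseline = 0. Since 0 < 15 and 0 < 20, no rule can be met. Enumeration over every integer in assumed ranges confirms it:

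| Variable | Range tried | Values | CS at baseline, Table 7 as written | Past a limit, absolute part only |
|---|---|---|---|---|
| Systolic | 60–260 | 201 | 0 | 112 |
| Diastolic | 30–160 | 131 | 0 | 77 |
| Pulse | 30–200 | 171 | 0 | 102 |

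The zeros do not depend on the ranges. The last column counts possible values, not expected patients; it shows only that the absolute part alone can be met at baseline.

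**Step 2: what the table would show.** Illustrative systolic readings:

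| Baseline | Week 8 | Change | Table 7 as written | Absolute part only |
|---|---|---|---|---|
| 155 | 182 | +27 | not CS to CS | below to above limit |
| 185 | 205 | +20 | not CS to CS | above to above limit |
| 185 | 190 | +5 | not CS to not CS | above to above limit |
| 185 | 155 | −30 | not CS to not CS | above to below limit |

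The first two patients fall in the same cell, although one was past the limit before treatment. Only two of the four cells of the shift table can ever be filled.

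**Step 3: readings available on therapy.** Vital signs for analysis are taken at three visits: Baseline, Week 8 Session 2 before light, and End of Study. That leaves 3 − 1 = 2 post-baseline readings. If 'on-therapy' excludes End of Study, 2 − 1 = 1 reading remains, so minimum = maximum for every patient and End of Study drops out of this display. If it includes End of Study, there are two readings and they can differ. The SAP does not say which applies.

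**Step 4: a rule elsewhere.** Neither document gives an absolute-only flag for baseline. The protocol's screening vital signs do not help, because SAP 7.3 fixes the Baseline visit as the reference.

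**The case against.** The best defence is that the table still does the main job of a safety display. A patient going from 155 to 182 is correctly shown as newly CS, and the joint criterion is meant to ignore values that were already extreme. Vital-sign values and changes from Baseline are summarised (SAP 7.3), and every value is listed (after SAP Table 7). Protocol 10.2 adds per-patient listings, means and medians, and highlighting of outliers. With about 6 patients, any extreme baseline can be read directly from a listing.

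Most of this stands, and it rules out several stronger readings that a reader might infer:
- That the table can show no shift at all. It can show not CS to CS; what it cannot show is any movement from CS at baseline.
- That every patient is declared normal at baseline. The label is 'not CS', which is a different statement.
- That leaving 185 to 190 unflagged is in itself a fault of the joint criterion. A rule for new change is entitled to pass over it. The difficulty is that the shift table has no other place to record that the patient was past the limit at both visits.
- That minimum always equals maximum, or that End of Study is not on therapy. These depend on an undefined window. The concomitant-medication window in SAP 5.7 runs to 14 days after last study medication, and the treatment-emergent definition in SAP 7.1 sets no cut-off at last dose, so a window that includes End of Study is possible.
- That follow-up data are lost. At most, End of Study is missing from this one display.

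The defence does not reach the central point. SAP 7.3 explicitly asks for a CS-at-baseline count, and its only definition makes that count zero. The column heading 'Absolute Value' may hint at an absolute-only intention, but every rule beneath it says otherwise.

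**Conclusion.** The point holds. As written, the CS-at-baseline row is zero for systolic pressure, diastolic pressure and pulse, by subtraction alone and with no assumption about the data. The display therefore amounts to a count of post-baseline joint-criterion values and cannot distinguish pre-existing from new abnormality. Separately, the on-therapy window is undefined and refers to cycles that the design does not have. The equality of minimum and maximum is conditional on End of Study being excluded.

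The consequence is small: one descriptive safety table in about 6 patients (up to 8 in total with replacement, protocol 5.4). The primary endpoints, ECG and hypericin levels, are unaffected, and all readings remain in the listings and summaries. It is still worth correcting, because a stated rule gives a misleading classification. The SAP prevails over the protocol on planned analyses (SAP Introduction), so no protocol text repairs it.

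**What to change.** In SAP 7.3:
- For the shift table, classify each value by the absolute part of the existing Table 7 limits only, at Baseline, Week 8 and End of Study, and show the shift from Baseline to each later visit.
- Report the joint criterion (limit plus change) separately, as the number of patients meeting it at Week 8 and at End of Study.
- Replace the wording on minimum and maximum values, treatment cycles and on-therapy with those two named visits.

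This uses the sponsor's own limits and takes no position on whether they are clinically right. It needs no new data and no protocol change. The cost is a few lines of SAP wording and one table shell.

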**Table 7: Vital Signs Clinically Significant Values**

Vital Sign Variable	Absolute Value
Systolic Blood Pressure	$\geq 180$ mmHg and increase of $\geq 20$ mmHg from baseline $\leq 90$ mmHg and decrease of $\geq 20$ mmHg from baseline
Diastolic Blood Pressure	$\geq 105$ mmHg and increase of $\geq 15$ mmHg from baseline $\leq 50$ mmHg and decrease of $\geq 15$ mmHg from baseline
Pulse	$\geq 120$ bpm and increase of $\geq 15$ bpm from baseline $\leq 50$ bpm and decrease of $\geq 15$ bpm from baseline

Listings of all vital sign values will be presented.

#### 7.4. Extent of Exposure

The number of exposures of drug applications and phototherapy for the study population will be summarized by frequency table. Descriptive statistics will be provided.

## 8. APPENDIX 1: DATA HANDLING CONVENTIONS

### 8.1. Missing Severity Assessment for Adverse Events

If severity is missing for an AE started prior to the first study medication, then a severity of “Mild” will be assigned. If the severity is missing for an AE started on or after the first study medication dosing, then a severity of “Severe” will be assigned. The imputed values for severity assessment will be used for incidence summary, while the actual missing values will be presented in data listings.

### 8.2. Missing Relationship to Study Drug for Adverse Events

If the relationship to the study medication is missing for an AE started after baseline, a causality of “Related” will be assigned. The imputed values for relationship to study medication will be used for incidence summary, while the actual values will be presented in data listings.

### 8.3. Missing Date Information for Adverse Events

The following imputation rules only apply to the case where the date is incomplete (i.e., partial missing) for adverse events. *Missing day and month*

- If the year is same as the year of first day on study medication, then the day and month of the start date of study medication will be assigned to the missing fields.
- If the year is prior to the year of first day on study medication, then December 31 will be assigned to the missing fields.
- If the year is after the year of first day on study medication, then January 1 will be assigned to the missing fields.

*Missing month only*

- Treat day as also missing and replace both month and day according to the above procedure.

*Missing day only*

- If the month and year are same as the year and month of first day on study medication, then the start date of study medication will be assigned to the missing day.
- If the month and year are before the year and month of first day on study medication, then the last day of the month will be assigned to the missing day.
- If the month and year are after the year and month of first day on study medication, then the first day of the month will be assigned to the missing day.

If the stop date is complete and the imputed start date as above is after the stop date, the start date will be imputed by the stop date.

## 8.4. Missing Date Information for Prior or Concomitant Medications

For prior or concomitant medications, including rescue medications, incomplete (i.e., partial missing) start date and/or stop date will be imputed. When the start date and the stop date are both incomplete for a patient, impute the start date first.

- **Incomplete Start Date**

The following rules will be applied to impute the missing numerical fields. If the stop date is complete and the imputed start date is after the stop date, then the start date will be imputed using the stop date.

*Missing day and month*

- If the year of the incomplete start date is the same as the year of the first dose date of study medication, then the day and month of the first dose date will be assigned to the missing fields.
- If the year of the incomplete start date is prior to the year of the first dose date of study medication, then December 31 will be assigned to the missing fields.
- If the year of the incomplete start date is after the year of the first dose date of study medication, then January 1 will be assigned to the missing fields.

*Missing month only*

- Treat day as also missing and replace both month and day according to the above procedure.

*Missing day only*

- If the month and year of the incomplete start date are the same as the month and year of the first dose date of study medication, then the day of the first dose date will be assigned to the missing day.
- If either the year is before the year of the first dose date of study medication or if both years are the same but the month is before the month of the first dose date of study medication, then the last day of the month will be assigned to the missing day.
- If either the year is after the year of the first dose date of study medication or if both years are the same but the month is after the month of the first dose date of study medication, then the first day of the month will be assigned to the missing day.

- **Incomplete Stop Date**

The following rules will be applied to impute the missing numerical fields. If the last dose date of study medication is missing, replace it with the last visit date. If the imputed stop date is before the start date (imputed or non-imputed start date), then the imputed stop date will be equal to the start date.

*Missing day and month*

*If the year of the incomplete stop date is the same as the year of the last dose date of study medication, then the day and month of the last dose date will be assigned to the missing fields.*

- If the year of the incomplete stop date is prior to the year of the last dose date of study medication, then December 31 will be assigned to the missing fields.
- If the year of the incomplete stop date is after the year of the last dose date of study medication, then January 1 will be assigned to the missing fields.

*Missing month only*

- Treat day as also missing and replace both month and day according to the above procedure.

*Missing day only*

- If the month and year of the incomplete stop date are the same as the month and year of the last dose date of study medication, then the day of the last dose date will be assigned to the missing day.
- If either the year is before the year of the last dose date of study medication or if both years are the same but the month is before the month of the last dose date of study medication, then the last day of the month will be assigned to the missing day.
- If either the year is after the year of the last dose date of study medication or if both years are the same but the month is after the month of the last dose date of study medication, then the first day of the month will be assigned to the missing day.

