## 5.7. Prior and Concomitant Medications

The World Health Organization Drug Dictionary (WHO Drug) will be used to classify prior and concomitant medications by therapeutic class and generic name based on ATC code level 3. Prior medication is defined as any medication taken prior to the first dose of the study medication. Concomitant medication is defined as any medication taken between the day of first dose of the study medication and the day of last study medication date + 14 days.

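### For one pattern of partial dates, SAP 8.4 classes a medication whose recorded stop month is before dosing as concomitant and not prior

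*SAP*

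**What the plan says.** SAP 8.4 sets the order of work for medications with two partial dates: "When the start date and the stop date are both incomplete for a patient, impute the start date first". The rules that matter here are these.

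- **Start with day and month missing, year equal to the year of first dose:** "then the day and month of the first dose date will be assigned to the missing fields".
- **Start with only the month missing:** "Treat day as also missing and replace both month and day according to the above procedure". It therefore also becomes the first-dose date.
- **Cap on an imputed start:** it applies only "If the stop date is complete and the imputed start date is after the stop date". The start is then set to the stop date.
- **Stop with only the day missing, in a month before the last-dose month:** set to the last day of that month.
- **Imputed stop before the start, whether the start is recorded or imputed:** "then the imputed stop date will be equal to the start date".

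SAP 5.7 uses the resulting dates. Prior means taken before the first dose. The other class is worded: "Concomitant medication is defined as any medication taken between the day of first dose". It runs to 14 days after the last dose, and the first-dose day itself counts.

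SAP 8.3, for adverse events, has a cap of the same kind ("If the stop date is complete and the imputed start date as above is after the stop date") but no rule for imputing a stop date.

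**The concern.** A recorded stop month before the first-dose month settles the question of class: whatever the missing day is, the drug ended before dosing. The SAP already accepts that a stop date should limit an imputed start, but it applies that limit only when the stop date is complete. With a partial stop date the conflict is resolved the other way: the recorded month gives way to an assumed start.

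At stake is the accuracy of the medication summaries. A drug taken only before the study would leave the prior class and appear as used on the first day of dosing. Protocol 10.2 also asks for a tabulation of medications received during the 10-week period, where the record could reappear. SAP 8.1, 8.2 and 8.5 say that actual values go into the listings. SAP 8.4 says nothing on this, so a reader of the output might not see that a recorded month had been replaced.

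**Working it through.** The plan gives no figure to reproduce. The check is to apply the rules literally to example records.

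**Inputs**
- Imputation rules: SAP 8.4. Classification: SAP 5.7.
- First dose 2 May 2022. This is an assumption, set to the date of first enrollment in the protocol synopsis, because no patient-level dose dates are given.
- Last dose 24 June 2022, an assumption consistent with 8 weeks of treatment.

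**Record in the pattern: start 2022, stop Apr 2022**
1. Start: the month is missing and the year is the dosing year, so it becomes 2 May 2022.
2. Cap: the stop date is not complete, so the cap does not apply.
3. Stop: the day is missing and April is before the last-dose month, so it becomes 30 Apr 2022.
4. Conflict: 30 Apr is before 2 May, so the stop is raised to 2 May 2022.
5. Class: use begins and ends on the first-dose day, so the drug is concomitant and not prior.

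**Comparison records, same assumed dates**

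| Start recorded | Stop recorded | Dates after SAP 8.4 | Class |
|---|---|---|---|
| 2022 | Apr 2022 | 2 May to 2 May 2022 | concomitant only |
| 2022 | Mar 2022 | 2 May to 2 May 2022 | concomitant only |
| 2022 | 15 Mar 2022 | 15 Mar to 15 Mar 2022 | prior |
| Feb 2022 | Mar 2022 | 28 Feb to 31 Mar 2022 | prior |
| 10 Feb 2022 | Mar 2022 | 10 Feb to 31 Mar 2022 | prior |
| 2021 | Mar 2022 | 31 Dec 2021 to 31 Mar 2022 | prior |
| 2022 | May 2022 | 2 May to 31 May 2022 | concomitant |

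Rows 2 and 3 show the inconsistency: less detail about the day changes the class, although every day in March is before dosing. The last row is not an error. A stop in May may fall after the first dose, and treating that uncertainty as concomitant use is reasonable.

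**Is the trigger exactly this narrow?** The rules were coded and run on a grid of true start and stop dates from January 2021, every third day, with all stops before May 2022. The start was masked three ways (complete, day missing, day and month missing) and the stop two ways (complete, day missing). Each of the 3 × 2 = 6 masks has 7,503 + 4,880 + 820 = 13,203 pairs. All 820 pairs with a 2022 start lacking day and month and a stop lacking its day came out concomitant only. No other pair did. Because the rule is deterministic, 820 of 820 defines the trigger. It says nothing about how often such records arise.

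**Check of the fix.** The latest possible date of Apr 2022 is 30 Apr 2022, which is before the imputed start of 2 May. The start becomes 30 Apr, the stop is imputed as 30 Apr, and the drug is prior. For a stop of Mar 2022 both dates become 31 Mar 2022, also prior. On the grid, no pair is then classed as concomitant. The stop in May 2022 keeps its class, because its latest possible date, 31 May, is not before 2 May.

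**The case against.** The strongest case on the other side is that the pattern hardly arises. Protocol 7.6 collects prior medications back to 3 weeks before screening, and Protocol 5.3.1 places screening within 28 days before Baseline, when the first application takes place. The window therefore opens at most 21 + 28 = 49 days before first dose. A site able to place a drug inside that window will often know the day it stopped. The exclusion criteria also turn on intervals of 2 and 3 weeks, so the dates of washout drugs should receive the closest attention. This is a good argument that the frequency is low, and it stands.

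It does not empty the pattern. With a first dose on 2 May 2022 the window can open on 14 March, so a stop in April or late March is inside it. With a first dose on 13 June, a stop recorded as May 2022 is well inside.

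A second argument is that leaning towards concomitant is ordinary caution. That holds where the true class is uncertain, but here the recorded month rules out use after dosing.

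Several stronger readings are tempting, and the documents do not support them.

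- **Every drug stopped in a month before dosing is misclassified.** The comparison records show otherwise.
- **Washout drugs are the most likely to be hit, and false protocol deviations follow.** Nothing in the documents says these drugs have poorer dates. The SAP derives no deviations from imputed dates, and its only analysis population is all enrolled patients (SAP 5.2), so nobody would be excluded. Concomitant use of a photosensitizer is not in itself a violation, since the protocol allows stable use without photosensitivity.
- **One record moves a table row by about 17 percentage points.** That is 1/6 with 6 patients, but SAP 5.7 specifies no percentage table and SAP 5 summarises categorical data as counts.
- **Adverse events are equally affected.** SAP 8.3 shares the cap but imputes no stop date. SAP 7.1 collects events from first administration, and Protocol 8.1.1 sends conditions present at first dose to medical history. Little room is left for the error.

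**Conclusion.** Wrong as written, with minor severity. The error needs three things together: a start date without its month, a start year equal to the dosing year, and a stop date with month and year but no day, in a month before the first-dose month. For such a record the literal rules give the wrong class every time, and no other rule in either document prevents it. Any other combination with a stop known to precede dosing is classed correctly.

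The number of affected records cannot be stated. The documents give no figure, and with about 6 patients and a short collection window it is probably low and may be zero. The effect is confined to the prior and concomitant medication summaries. The planned ECG, hypericin and adverse event analyses do not use this classification, so nobody should infer a threat to the primary endpoints.

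The conclusion rests on a literal reading of SAP 8.4 and 5.7. The calendar dates in the examples are assumptions, but the mechanism does not depend on them.

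**What to change.** In SAP 8.4, replace the cap that works only with a complete stop date by: *If the latest possible date of the recorded stop date (complete or partial) is before the imputed start date, set the start date to that latest possible stop date.*

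Keep the existing rule that raises an imputed stop to the start, unchanged and for all records. It should not be limited to complete start dates. With a last dose on 24 June 2022, a start of Jul 2022 is imputed as 1 July and a stop of 2022 as 24 June. The new cap does not fire, because the latest possible stop is 31 December. Without the fallback the record would end before it began; with it, the record is 1 July to 1 July.

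Applying the same cap in SAP 8.3 is optional, for consistency.

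The cost is one sentence in SAP 8.4 (and one in 8.3 if wanted) and a small programming change. No further data are needed.
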